## Consort Flow diagram of Ivermectin prophylaxis trial

## **Statistical analysis**

All data were collected, tabulated and statistically analyzed using SPSS 22.0 for windows (IBM Inc., Chicago, IL, USA) and MedCalc 13 for windows (MedCalc Software Bvba, Ostend, Belgium). Continuous Quantitative variables were expressed as the mean  $\pm$  SD & median (range), and categorical qualitative variables were expressed as absolute frequencies (number) & relative frequencies (percentage). Continuous data were checked for normality by using Shapiro Walk test. Mann-Whitney U test was used to compare between two groups of non-normally distributed data. Categorical data were compared using Chi-square test or Fisher's exact test when appropriate. Relative risk and its 95%Confidence interval (CI) was calculated to estimate risk of COVID-19 infection in addition forest plot was plotted. Univariate and multivariate binary logistic regression were built to find predictors for COVID-19 protection. All tests were two sided. p-value < 0.05 was considered statistically significant.

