### **Materials and Methods:**

**Study Design** interventional study

**Sample Size:** Family close contacts to 50 patients diagnosed as having COVID-19 by RT-PCR

**Location:** Isolation facilities/Zagazig University Hospitals

**Inclusion:** Age more than 16 years, Asymptomatic household close contacts

**Exclusion:** people previously treated for COVID-19, asymptomatic contacts with who have HRCT chest done and suggestive for COVID-19 infection

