### **Intervention :**

All documented asymptomatic family contacts, starting on day of diagnosis of their index case will receive Ivermectin according to body weight as follows:

40-60 kg : 15 mg

60 -80 kg :18 mg

> 80 kg : 24 mg

This will be given as one dose at day one (diagnosis day), repeated once at day 3

In literature, individuals can receive 600mcg per Kg of ivermectin daily for 3 days without side effects (9,10)

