## Results

As regard index cases, there were 9 (11.8%) mild , 44 (57.9%) moderate and 23 (30.3%) severe cases. In the ivermectin group, there were 8 (53.3%) mild , 6 (40%) moderate and 1 (6.7%) severe cases. While in the no-intervention group, there were 31 (52.5) mild, 21 (35.6%) moderate and 7 (11.9%) cases.

[figure not shown]

Figure (1): Scatter plot shows relationship between contact time in days and number of contacts that developed COVID-19; dashed line represent best fitted line (quadratic model).

There was insignificant linear correlation between contact time in days and number of contact that developed COVID-19. The appropriate forecasting for number of contact that developed COVID-19 based upon contact time in days was quadratic model.

[figure not shown]

Figure (2): Box plot shows relationship between isolation and number of contacts that developed COVID-19.

There was insignificant difference between index cases isolated at hospital and index cases isolated at home regarding number of contact that developed COVID-19 where mean number of contact that developed COVID-19 ( $\pm$ SD) was 2.14 ( $\pm$ 1.35) versus 2.07 ( $\pm$  2.26) respectively (p-value=0.280)

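### The contact-level tests and models ignore clustering of contacts by index case, so precision is overstated for index-case severity, and for arm if families share an arm

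*Combined protocol and SAP*

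**What the plan says.** The sample is defined through index patients, not as individuals: "Family close contacts to 50 patients diagnosed as having COVID-19 by RT-PCR" (Materials and Methods, Sample Size). The Intervention section treats the family as a group: "All documented asymptomatic family contacts, starting on day of diagnosis of their index case will receive Ivermectin". It describes no control arm and no unit of allocation.

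The Statistical analysis section names four kinds of comparison, all of which assume independent observations:

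- "Categorical data were compared using Chi-square test or Fisher's exact test when appropriate"
- "Mann-Whitney U test was used to compare between two groups of non-normally distributed data"
- "Relative risk and its 95%Confidence interval (CI) was calculated to estimate risk of COVID-19 infection"
- "Univariate and multivariate binary logistic regression were built to find predictors for COVID-19 protection"

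The readable text contains no household term, random effect, GEE, robust standard error or intracluster correlation (ICC).

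On index cases, the Results state that "there were 9 (11.8%) mild , 44 (57.9%) moderate and 23 (30.3%) severe cases", which makes 76. Tables 1 and 2 analyse 203 + 101 = 304 contacts. Tables 3 and 4 use index-case severity as a stratifier and as a predictor of each contact's outcome.

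**The concern.** Contacts in one household share an index case, an exposure and a home, so their outcomes are likely to be correlated. Standard errors that ignore this are too small for any factor that is constant within the family. Index-case severity is such a factor by definition. Arm is one only if whole families were given the same arm.

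The printed intervals and p-values for these factors would then be too optimistic. The results with least room are the moderate-severity predictor in Table 4 (p = 0.006), the mild-index stratum in Table 3 (p = 0.001, resting on 9 index cases) and days until symptoms in Table 2 (p = 0.017).

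**Working it through.** **1. Cluster size.** 304/76 = 4.0 contacts per index case. By severity, the contact counts rebuilt from the Table 3 percentages are 34, 178 and 92, against 9, 44 and 23 index cases: 34/9 = 3.8, 178/44 = 4.0, 92/23 = 4.0. The near-constant ratio supports the inference that these 76 index cases produced the 304 contacts. No sentence says so.

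**2. Reproducing the printed tests.** Pearson chi-square without continuity correction, one row per contact:

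| Comparison | Protected, ivermectin | Protected, control | Recomputed | Printed |
|---|---|---|---|---|
| Overall | 188/203 | 42/101 | 95.351 | 95.351 |
| Mild index case | 13/14 | 7/20 | 11.381 | 11.381 |
| Moderate | 129/135 | 24/43 | 42.666 | 42.666 |
| Severe | 46/54 | 11/38 | 29.928 | 29.928 |

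The arm tests were therefore run as if contacts were independent.

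**3. Design effect.** The documents give neither an ICC nor a family-size distribution, so both are assumed here. DEFF = 1 + (4(1 + CV²) − 1) × ICC.

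| Assumed CV of family size | ICC | DEFF | Effective n (304/DEFF) |
|---|---|---|---|
| 0 | 0.05 | 1.15 | 264 |
| 0 | 0.3 | 1.90 | 160 |
| 0.5 | 0.05 | 1.20 | 253 |
| 0.5 | 0.3 | 2.20 | 138 |

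**4. Index severity, moderate against severe (Table 4, adjusted).** OR 2.816 (1.355–5.851) implies SE = [ln 5.851 − ln 1.355]/3.92 = 0.373 and z = 2.774, so p = 0.0055, which matches the printed 0.006. Dividing z by √DEFF gives p = 0.010 (ICC 0.05) to 0.044 (ICC 0.3) with equal families, and 0.061 at ICC 0.3 with CV 0.5. The p-value reaches 0.05 at DEFF = (2.774/1.96)² = 2.00. That is an ICC of about 1.00/3 = 0.33 with equal families, or 1.00/4 = 0.25 with CV 0.5.

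The Table 4 model cannot be rebuilt, so this is illustrative. A logistic model with arm and severity only, rebuilt from the counts in step 2, gives moderate OR 3.36 (1.65–6.88), SE 0.365, z 3.32. Its p-value becomes 0.002–0.016 with equal families and 0.025 at ICC 0.3 with CV 0.5.

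**5. Arm, if families share an arm.**

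- Chi-square: 95.351/1.15 = 82.9; /1.90 = 50.2; /2.20 = 43.3. All p<0.001.
- Relative risk (not printed in the readable text): (15/203)/(59/101) = 0.126, SE of the log 0.262, CI 0.076–0.212. With SE × √DEFF the CI is 0.073–0.220 at ICC 0.05, 0.062–0.257 at ICC 0.3, and 0.059–0.271 at ICC 0.3 with CV 0.5.
- Mild stratum: DEFF = 1 + 2.78 × ICC, so 11.381 becomes 9.99 (ICC 0.05) and 6.21 (ICC 0.3). Against F(1,7), for 9 index cases in two arms, p = 0.016 and 0.042. The F reference alone, at ICC 0, gives 0.012.
- Days until symptoms: z = 2.391, so a DEFF of (2.391/1.96)² = 1.49 takes p = 0.017 past 0.05.
- No inflated interval is given for the adjusted arm OR. Its printed SE (0.483) does not match the rebuilt arm + severity model (0.349).

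**6. A denominator that does not fit.** The Figure 2 text compares infected contacts per index case by place of isolation ("There was insignificant difference between index cases isolated at hospital and index cases isolated at home regarding number of contact that developed COVID-19"), with means of 2.14 and 2.07. Table 2 gives 15 + 59 = 74 infected contacts, and 74/76 = 0.97. Means near 2.1 would need about 74/2.1 ≈ 35 index cases.

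**The case against.** **The main result survives.** It does, throughout the ranges above, so the matter is one of stated precision.

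**The link from 76 index cases to 304 contacts is inferred, and the plan names 50.** This stands as a limit on the figures. Clustering itself does not depend on the link, because contacts were recruited through index cases whatever their number. With 50 index cases the mean would be 304/50 = 6.08 and the DEFF 1 + 5.08 × ICC = 1.25–2.52. That gives a main chi-square of 76.0–37.8 and a moderate-severity p of 0.013–0.081: a larger effect, not a smaller one.

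**The arm part depends on an allocation unit that is not stated.** This stands. The Intervention section suggests whole-family treatment but describes only one arm, and the flow diagram is not in the readable text. If arms were mixed within families, arm precision would not be overstated in this way.

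**The secondary results are less fragile than they look.** Partly right. With equal families the moderate-severity p-value stays below 0.05 across the assumed ICC range, and in the rebuilt model it stays below in every case tried. Moreover, the ICC that matters for an adjusted result is the residual one. In the mild stratum much of the shift comes from the F reference; on plain chi-square p would be 0.002–0.013. For days until symptoms only 74 contacts enter the test. With equal clusters of about 2.1, a DEFF of 1.49 needs an ICC of 0.49/1.1 ≈ 0.44, above the assumed range. That item is the least certain.

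**Table 4 has another fault.** Its univariate ORs are within-group odds: 188/15 = 12.533 and 153/25 = 6.120. Those rows are wrong before clustering arises. This is a separate correction and does not excuse the omission here.

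**Conclusion.** The concern holds. The analysis uses only independent-contact methods on family-clustered data, and exact reproduction of the four chi-squares confirms this for the arm tests. Precision for index-case severity is overstated under any positive within-family correlation. Precision for arm is overstated in the same way if families share an arm.

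The sizes rest on an assumed ICC of 0.05–0.3, about 4 contacts per index case, and a design-effect approximation. On that basis, intervals for family-level factors should be wider by a factor of √1.15 = 1.07 to √1.90 = 1.38 on the log scale, or up to √2.20 = 1.48 with unequal families. The main arm difference remains significant. The secondary p-values should not be relied on as printed. Nothing is claimed for contacts over 60, because their spread over families is not given. This should be fixed; confidence is high that the method is missing, and lower for the exact magnitudes.

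**What to change.** - Name the index case as the cluster in the Statistical analysis section. Replace the contact-level arm tests, relative-risk CI and logistic models with GEE (log link for RR, logit for OR, exchangeable correlation, small-sample-corrected robust SE) or a mixed model with a random intercept per index case. Choose one as primary, since GEE gives a marginal OR and the random-intercept model a conditional one.
- Use a cluster-aware test for days until symptoms.
- Present the mild-index stratum descriptively. With 9 index cases and one infected contact in the ivermectin arm (13/14 protected), a model there will not be stable.
- State whether allocation was by family or by contact. Report the ICC, the family sizes, and the number of index cases per arm and per severity stratum beside the number of contacts.
- First reconcile the means of 2.14 and 2.07 infected contacts per index case with 74/76 = 0.97, and state the denominator used.

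The cost is a change of wording and a re-run on data already held, provided the index-case identifier was kept. The Figure 2 analysis counts infected contacts per index case, so it should exist. Intervals will become somewhat wider.

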**Table (1): Comparison between Ivermectin arm and non-intervention arm regarding basic characteristics.**

| Basic characteristics  | Ivermectin arm
(N=203) |       | Non-intervention arm
(N=101) |       | Test       | p-value |
|------------------------|---------------------------|-------|---------------------------------|-------|------------|---------|
|                        | No.                       | %     | No.                             | %     |            |         |
| Gender          |                           |       |                                 |       |            |         |
| Male                   | 106                       | 52.2% | 50                              | 49.5% | 0.199a     | 0.656   |
| Female                 | 97                        | 47.8% | 51                              | 50.5% |            |         |
| Age (years)     |                           |       |                                 |       |            |         |
| Mean ± SD              | 39.75 ± 14.93             |       | 37.69 ± 16.95                   |       | -          | 0.175   |
| Median (Range)         | 38 (16 – 94)              |       | 35 (16 – 78)                    |       | 1.357
b |         |
| Any comorbidity |                           |       |                                 |       |            |         |
| Absent                 | 156                       | 76.8% | 75                              | 74.3% | 0.248a     | 0.619   |
| Present                | 47                        | 23.2% | 26                              | 25.7% |            |         |

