| Protection      | 188 | 92.6% | 42 | 41.6% | a       |        |

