**a: Chi-square test; b: Mann Whitney U test; p< 0.05 is significant.**

**Table (2)** shows that 15 contacts (7.4%) developed COVID-19 in the ivermectin arm compared to 59 (58.4%) in the no-intervention arm, all of them were symptomatic, according to the study protocol . The difference was highly significant ( $p<0.001$ ). The median (range) days for developing the disease was 2 (2-6) in ivermectin group compared and 4 (2-10) in the no-intervention group, the difference was significant ( $p<0.017$ ). Ten contacts (66.6%) developed symptoms in 1st 3 days in ivermectin group, and none developed it after 6 days. In the no-intervention arm, 25 (42.3%) developed symptoms in the 1st 3 days and continued to the 10 days.

HRCT of the chest was performed in 14 out 15 contacts and in 58 of the 59 contacts who developed symptoms in ivermectin and no-intervention groups, respectively. The missed one case in each arm had symptoms and positive RT-PCR without other investigations. Chest HRCT was positive for

COVID-19 in 7 (50%) and 28 (48.3%) in ivermectin and no-intervention groups, respectively.

Complete blood count was performed also in 14 and 58 contacts who developed symptoms in ivermectin and no-intervention groups respectively. Positive criteria in CBC was present in 12 (85.7%) and 53 (91.4%) in ivermectin and no-intervention groups respectively.

**Table (3): Comparison between Ivermectin arm and non-intervention arm regarding protection rate stratified by basic characteristics.**

|                     |          | Protection rate |                      | Testa  | p-value |
|---------------------|----------|-----------------|----------------------|--------|---------|
|                     |          | Ivermectin arm  | Non-intervention arm |        |         |
| All patients        |          | 92.6%           | 41.6%                | -----  | -----   |
| Index case severity | Mild     | 92.9%           | 35%                  | 11.381 | 0.001   |
|                     | Moderate | 95.6%           | 55.8%                | 42.666 | <0.001  |
|                     | Severe   | 85.2%           | 28.9%                | 29.928 | <0.001  |
| Age                 | ≤60      | 93.8%           | 41.3%                | 91.514 | <0.001  |
|                     | >60      | 84%             | 44.4%                | 5.320  | 0.034   |
| Gender              | Male     | 94.3%           | 42%                  | 53.482 | <0.001  |

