**Table (4): Predictors for COVID-19 protection.**

|                            | Univariate Model      |         | Multivariate Model    |         |
|----------------------------|-----------------------|---------|-----------------------|---------|
|                            | OR (95%CI)            | p-value | OR (95%CI)            | p-value |
| Arm                 |                       |         |                       |         |
| Ivermectin                 | 12.533 (7.408-21.205) | <0.001  | 11.445 (4.444-29.475) | <0.001  |
| Non-intervention           | Reference             |         |                       |         |
| Index case severity |                       |         |                       |         |
| Mild                       | 1.429 (0.722-2.828)   | 0.306   | 1.257 (0.486-3.247)   | 0.637   |
| Moderate                   | 6.120 (4.010-9.341)   | <0.001  | 2.816 (1.355-5.851)   | 0.006   |

| Severe          | Reference           |        |                     |       |
|-----------------|---------------------|--------|---------------------|-------|
| <hr/>           |                     |        |                     |       |
| Age             |                     |        |                     |       |
| Age≤60 years    | 3.154 (2.386-4.169) | <0.001 | 0.254 (0.101-0.639) | 0.004 |
| Age>60 years    | Reference           |        |                     |       |
| <hr/>           |                     |        |                     |       |
| Gender          |                     |        |                     |       |
| Male            | 3.457 (2.373-5.036) | <0.001 | 0.836 (0.437-1.600) | 0.588 |
| Female          | Reference           |        |                     |       |
| <hr/>           |                     |        |                     |       |
| Any comorbidity |                     |        |                     |       |
| Absent          | 3.812 (2.774-5.239) | <0.001 | 2.222 (0.967-5.108) | 0.060 |
| Present         | Reference           |        |                     |       |

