**OR: Odds Ratio; 95%CI: 95%Confidence Interval.**

**Table (5)** shows that ivermectin have very highly significant role in the protection of SARS-CoV-2 infection. . It has an OR of 12.533 and 11.445 when compared to no intervention in both univariate and multivariate models, respectively. Ivermectin protection was not affected by gender or comorbidities in multivariate model.

As regard ivermectin side effects, they were reported in 11 (5.4%) contacts. These were; diarrhea (1.5%), nausea (1%), fatigue (1%), sleepiness (0.5%), abdominal pain (0.5%), heart burn (0.5%), tingling and numbness (0.5%) and lastly burning sensation (0.5%)

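### The relative risk of infection that the analysis section says was calculated is not in the readable results; the closing summary gives odds ratios of protection instead, and one of them, 12.533, does not compare the two arms.

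*Combined protocol and SAP*

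**What the plan says.** The Statistical analysis section names a measure of effect and a model:

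- On the effect measure: "Relative risk and its 95%Confidence interval (CI) was calculated to estimate risk of COVID-19 infection in addition forest plot was plotted".
- On the model: "Univariate and multivariate binary logistic regression were built to find predictors for COVID-19 protection".

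The Results give the risks by arm. The text under Table (2) reads "15 contacts (7.4%) developed COVID-19 in the ivermectin arm compared to 59 (58.4%) in the no-intervention arm", and the protection row of Table (2) gives the complement, "188 | 92.6% | 42 | 41.6". The denominators are 203 and 101.

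Table (4) prints "12.533 (7.408-21.205" as the univariate odds ratio for ivermectin and 11.445 (4.444 to 29.475) as the multivariate one. The text under Table (4), which calls the table number 5, summarises the effect as follows: "It has an OR of 12.533 and 11.445 when compared to no intervention in both univariate and multivariate models, respectively".

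**The concern.** The section commits to a relative risk of infection with an interval. The only effect estimates with intervals in the readable results are logistic odds ratios, and they are for the opposite outcome, staying well. That outcome occurred in 41.6% of one arm and 92.6% of the other. At such frequencies an odds ratio is far from a ratio of risks, and a reader who takes 12.5 or 11.4 as a multiple of the chance of protection is misled.

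There is a second problem. The counts in Table (2) do not give 12.533 as an odds ratio between arms. If the first of the two headline figures is not a comparison of arms, the summary should not present it as one.

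**Working it through.** **Inputs.** From Table (2): ivermectin 188 protected and 15 ill (203); no intervention 42 protected and 59 ill (101). Tests are two-sided at 0.05, so intervals are 95%.

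**1. The counts are sound.** The uncorrected Pearson chi-square on 188/15 against 42/59 is 95.351, as printed in Table (2).

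**2. Reproducing 12.533.**
- Odds ratio between arms: (188 × 59)/(15 × 42) = 11,092/630 = 17.61. The standard error of its log is √(1/188 + 1/15 + 1/42 + 1/59) = 0.336, giving 9.12 to 34.00. This is not the printed figure. A logistic model with an intercept gives the same 17.61 (9.12 to 34.00).
- Odds within the ivermectin arm: 188/15 = 12.533. The standard error of the log is √(1/188 + 1/15) = 0.268, giving 7.408 to 21.205. This matches Table (4) to every printed digit. A logistic model without an intercept returns exactly this.

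**3. The rest of the univariate column shows the same pattern.** Counts by category (protected/ill, both arms together) can be rebuilt from the percentages and chi-squares in Table (3) and the group sizes in Table (1).

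| Row | Odds within the category | Printed in Table (4) | Odds ratio against the reference |
|---|---|---|---|
| Age ≤60 | 205/65 = 3.154 | 3.154 | 3.154/(25/9) = 1.14 |
| Male | 121/35 = 3.457 | 3.457 | 3.457/(109/39) = 1.24 |
| No comorbidity | 183/48 = 3.8125 | 3.812 | 3.8125/(47/26) = 2.11 |
| Mild index case | 20/14 = 1.429 | 1.429 | 1.429/(57/35) = 0.88 |
| Moderate index case | 153/25 = 6.120 | 6.120 | 6.120/(57/35) = 3.76 |

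The printed intervals for these rows also match those of the within-category odds.

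**4. The measure the section names.**
- Relative risk of illness: (15/203)/(59/101) = 0.0739/0.5842 = 0.126. The standard error of the log is √(1/15 - 1/203 + 1/59 - 1/101) = 0.262, giving 0.076 to 0.212. The inverse is 7.9.
- Risk difference: 0.0739 - 0.5842 = -0.510, unpooled standard error 0.0524, giving -61.3 to -40.8 points.
- For comparison, relative risk of protection: (188/203)/(42/101) = 2.23. The standard error of the log is 0.120, giving 1.76 to 2.82.

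On the protection scale the crude odds ratio is therefore 17.61/2.23 = 7.9 times the relative risk.

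**5. The adjusted figure.** If 11.445 is taken as a valid odds ratio at a control protection rate of 0.416, the implied relative risk of protection is 11.445/(1 - 0.416 + 0.416 × 11.445) = 2.14. This is only a conversion; the model cannot be refitted without individual data.

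**6. Clustering.** The Results list 9 + 44 + 23 = 76 index cases for 304 contacts, an average of 4. The documents give no intracluster correlation ρ, so take the full range from 0 to 1. With equal groups of 4 (an assumption), the design effect 1 + 3ρ runs from 1 to 4, and the standard error of the log relative risk from 0.262 to at most 0.525. At that extreme the interval is 0.126 × exp(±1.96 × 0.525), or about 0.045 to 0.354. Unequal group sizes could widen it further.

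**The case against.** Four objections carry weight.

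- **The relative risk may have been reported.** The section says a forest plot was drawn, and figures are missing from the text under review. A reader might infer that the relative risk was never calculated or was withheld. The documents do not support that. What stands is that the readable text and tables lack it and that the written summary does not use it.
- **The risks are printed.** Table (2) and the text under Tables (2) and (3) give 7.4% against 58.4%, so anyone can form the ratio. This is correct, and it limits the complaint to the summary under Table (4) and to the lack of any between-arm risk contrast with an interval.
- **Logistic regression was stated in the section.** Reporting odds ratios from it follows the text. Replacing it with a model for relative risks is a preference, not the correction of an error.
- **The conclusion survives on every scale.** This also stands; the point concerns what is reported and how large it is said to be.

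A stronger reading is tempting: that the figures of 11 to 12 are an inflated version of a true difference of only about 2.2-fold. It fails on two counts. The relative risk named in the section is for infection, where the contrast is about 7.9-fold; 2.2 is the ratio for protection, which the section does not name. And 12.533 corresponds to no between-arm ratio; the odds ratio that goes with 2.23 is 17.6, which is larger than the printed value.

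**Conclusion.** The point holds as a reporting error with a wrong figure in the headline. The named measure, the relative risk of illness, is 0.126 (0.076 to 0.212), with a risk difference of -51.0 points (-61.3 to -40.8), and neither is in the readable results. The first of the two odds ratios in the summary is the odds within one arm; the crude odds ratio is 17.6 (9.1 to 34.0).

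That 12.533 is a within-arm odds follows from an exact match of estimate and interval. The omitted intercept is the likely cause, since it explains the category rows of the univariate column as well, but the documents do not show the model call. Whether the multivariate column shares the fault cannot be determined from the printed tables, so nothing here shows 11.445 to be wrong.

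The intervals assume independent contacts and will widen for clustering. Under the equal-group bound above, the relative risk still excludes 1. All figures are crude contrasts of the reported counts and do not address how contacts came to be in each arm.

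**What to change.** - In Table (2) and the text under Table (4), report the relative risk of symptomatic illness and the risk difference, each with a 95% interval that allows for clustering of contacts by index case (for example, robust standard errors by index case). The relative risk of protection, 2.23 (1.76 to 2.82 before clustering), may be shown beside them.
- Delete 12.533 as a comparison of arms. Refit the univariate column of Table (4) with an intercept, and check the specification of the multivariate model in the same run.
- If the logistic model is kept, label its result as an odds ratio for a common outcome, not to be read as a ratio of risks. An adjusted relative risk from a modified Poisson model is optional.
- If the forest plot already shows the relative risk, quote it in the text and confirm that it agrees with 0.126.

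The cost is a minor reanalysis of data already in hand and some rewording. Direction and significance of the comparison do not change.
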